1.0 RESEARCH OBJECTIVES

1.1 Study Rationale

Despite extensive literature characterizing cardiac structure, function and electrical conduction in sedentary patients with AF, no data exists in athletic populations with AF. Measurement of these parameters would provide insight into the mechanisms and pathophysiology of exercise-induced AF, as well as the functional consequences of paroxysmal AF in this cohort. These data may inform the management of AF in athletes who continue to train and provide the basis for developing prognostic indicators in a population at greater risk for AF development, particularly in middle-age. Accordingly, this study will examine cardiac function, specifically left ventricular and left atrial phasic function in the presence of paroxysmal AF in endurance trained athletes. Secondly, atrial electromechanical function will be assessed in athletes to further explore functional parameters that may provide prognostic value.

1.2 Objectives

1) to assess and compare left atrial phasic volumes and function (as measured by ejection fraction and strain) at rest and during submaximal exercise in middle-aged endurance trained athletes with AF and age-matched healthy endurance trained athletes without AF.

2) to compare atrial electromechanical delay (AEMD) in middle aged endurance-trained athletes with AF to age-matched healthy non-AF endurance trained athletes. An exploratory objective will be to determine whether there is a correlation between P-wave duration and AEMD.

1.3 Hypotheses

1) It is expected that left atrial strain will be impaired in athletes with AF compared to athletes without AF at both rest and during submaximal exercise- though impairments will be more pronounced during submaximal exercise. Specifically, it is hypothesized that left atrial (LA) reservoir function will be reduced in athletes with AF, as it is a strong predictor for AF.

2) It is expected that despite similar left atrial size, athletes with AF will have significantly prolonged AEMD compared to age-matched athletes without AF.

Additionally, it is hypothesized that P wave duration and AEMD will be correlated, suggesting AEMD may be a sensitive and precise measure for atrial fibrosis.

2.0 STUDY POPULATION

This will be a cross-sectional cohort study involving: Male endurance trained athletes who have been diagnosed with paroxysmal AF (AF-ET) and 2) and male endurance trained athletes without diagnosis or history of AF or AF symptoms (H-ET). The study will be limited to male participants given the higher prevalence of AF compared to females.

Global Inclusion Criteria: Participants eligible will be male endurance athletes (between ages of 45 and 65). Subjects will be life-long participants (20 years +) of prolonged, intensive endurance running, cycling, rowing or triathlons. Athletes must be involved in year-round training and competition (in at least one or more events per year). Unrestricted participation history of light-intensity activity (eg. golf, walking etc) will be allowed.

Inclusion Criteria for H-ET: This group will be a referent population that is recruited from an existing cohort from our previously conducted study ‘Cardiac Consequences of

Endurance Exercise.’ Participants who have had prescreening, completed a resting signal averaged ECG, cMRI and Holter monitoring will be eligible.

Inclusion Criteria for Athletes with AF: The same criteria of athletic training as the athletes without AF (H-ET) will be used. This cohort will be recruited on the basis of having being diagnosed with paroxysmal AF in the last four (4) years. Specific criteria for paroxysmal AF diagnosis are: an absence of consistent P waves, irregular fibrillatory waves, variation in RR intervals, and atrial tachycardia (350-600 bpm) lasting for longer than 30 seconds and terminating in 48 hours time. Diagnosis will be verified using clinical charts that include either ambulatory 12-lead ECG readings or Holter monitor detection of AF. Subjects will be included regardless of medical treatment for AF which may include rate and/or rhythm control, either chronically or acutely (‘pill-in-a-pocket’ upon onset of episodes). All participants must be in sinus rhythm during all assessments.

Global Exclusion Criteria: 1) >1 hour of resistance training per week (risk of concentric remodeling), 2) BMI < 20 kgm⁻² or > 25 kgm⁻², 3) treatment or prior diagnosis of coronary artery disease or cardiomyopathy, valvular disease, hypertension, heart failure, diabetes, history of thyroid disorder, diagnosis of sleep apnea, current/recent viral or chronic illness, chronic inflammatory disease, 4) recreational drug use or excessive alcohol consumption (using accepted standards) 5) previous or current smoking, 6) contraindication to MRI.

Exclusion Criteria specific for AF group: 1) presence of atrial flutter, 2) previous ablation, 3) cessation of exercise > 6 months post diagnosis of AF, 4) inability to provide verification of AF diagnosis.

2.2 Sample Size

The primary outcome measure for the first hypothesis is atrial reservoir function, as measured by myocardial strain imaging by echocardiography. There are no data describing atrial phasic function in athletes with AF. Accordingly sample size was determined using the average difference in reservoir strain in a cohort of middle aged (51.78 ± 6.83 years) patients with lone AF, compared to healthy middle aged (48.97 ± 7.65 years) controls with no presence of AF or other cardiovascular related disease. Left atrial reservoir strain was reported as: (29.01 ± 5.63 %) in patients with AF compared to (35.5 ± 4.77 %) in healthy adults. Accordingly, the mean difference between groups was 6.49 ± 5.2 . Thus, based on an alpha of 0.05 and power of 0.8, 11 participants are necessary in each group.

The primary outcome measure for the second hypothesis is AEMD. No previous literature has examined AEMD in endurance athletes, nor is there established reference values for healthy adults. Previous literature has demonstrated patients with paroxysmal AF to have significantly greater delays in inter-atrial EMD, as well as both left and right AEMD. However, it has been suggested that specifically intra-left AEMD is a significant marker for the development of AF, and was correlated to P-wave dispersion, left atrial diameter and left atrial area ⁽⁴⁵⁾. Accordingly, sample size was determined using the difference in left AEMD in a cohort of otherwise healthy middle-aged patients (48.3 ± 11.1 years) with lone AF compared to healthy middle-aged (45.2 ± 4.8 years) controls with no presence of lone AF. Left-atrial EMD was reported as: 21.8 ± 9.1 ms in AF patients and 14.1 ± 4.9 ms in controls (difference of 7.7 ± 7 ms). Thus, based on an alpha of 0.05 and power of 0.8, 15 participants are necessary in each group (n=30).

Accordingly, the more conservative calculation of 15 per group will be used. However, in our experience, poor imaging quality lead to unanalyzable data may occur in 10-15% of the sample, therefore we will recruit 17 per group to ensure adequate statistical power.

2.3 Recruitment

Healthy endurance athletes will be recruited from our email list serve of previous ‘Cardiac Consequences of Endurance Exercise’ participants. Interested participants will contact either the principal investigator or co-investigators through email or phone.

Subjects with AF will be recruited by advertisement to local athletic clubs, emails to the GTA cardiology community for referrals and word of mouth. We have considerable experience in the recruitment of healthy endurance and recreationally trained subjects from both cycling and running clubs within the GTA. In addition we will seek referrals from cardiology and electrophysiology practices within the GTA using existing collaborative ties at teaching hospitals and by personal communication. We also have access to contact information of several athletes with AF who were excluded from our previous study who expressed interest in participating in a research study should one arise. These individuals will be provided with an email recruitment advertisement in which they will be prompted to contact the investigators by telephone or email in interested.

Initial screening for major inclusion/exclusions will be performed by the student investigator by telephone. If there is interest in participating following a telephone discussion, an information package including the informed consent will be sent electronically if possible, and subjects will be requested to meet in the Heart Health

laboratory located within the Goldring Center for High Performance Sport at the University of Toronto to submit their informed consent, receive further information should there be additional questions and undergo the initial assessment.

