2.8 Data Analysis

All variables will be expressed as mean and standard deviation. Differences in outcome measures (AEMD, atrial phasic function, atrial dimensions) will be assessed using a series of independent t-tests between the athletes with AF and athletes without AF. A 2-way repeated measures analysis of variance (ANOVA) will be used to compare resting and exercise values between and within groups. Covariates will be included when appropriate, including age, years since AF diagnosis, and number of AF episodes. Atrial size and relation to ECG parameters may be studied for correlational analyses.

Significance will be set at $p < 0.05$. Analysis will be performed using SPSS software.

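### The controls are called age-matched, but no described procedure assures it, and age is adjusted for only at discretion; age should be a fixed term in the analysis

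*Combined protocol and SAP*

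**What the plan says.** Section 1.2 defines the comparator in objective 1 as "age-matched healthy endurance trained athletes without AF" and in objective 2 as "age-matched healthy non-AF endurance trained athletes". In section 1.3, hypothesis 2 says that "athletes with AF will have significantly prolonged AEMD compared to age-matched athletes without AF"; hypothesis 1 does not use the term.

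Section 2.0 sets one age rule for everybody: "Participants eligible will be male endurance athletes (between ages of 45 and 65" years). The criterion specific to controls concerns tests already done, not age: "Participants who have had prescreening, completed a resting signal averaged ECG, cMRI and Holter monitoring will be eligible".

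On recruitment, section 2.3 states: "Healthy endurance athletes will be recruited from our email list serve of previous" participants in the earlier study, and those interested make contact. Athletes with AF are found through athletic clubs, cardiology and electrophysiology referrals, word of mouth, and contacts excluded from the earlier study.

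Section 2.8 compares AEMD, atrial phasic function and atrial dimensions by independent t-tests, and rest with exercise by a two-way repeated-measures ANOVA. It then adds: "Covariates will be included when appropriate, including age", followed by years since AF diagnosis and number of AF episodes.

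**The concern.** Age-matching is a design property. A reader of the final report would take it to mean that controls were chosen to resemble the athletes with AF in age. A common eligibility range restricts age, but within a 20-year span the two groups can still have different age distributions. They arrive by different routes, so there is no design reason to expect the same distribution.

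If the groups differ systematically in age, and strain or AEMD varies with age, an unadjusted comparison counts part of the age effect as an effect of AF. The analysis section does not close this gap. An independent t-test has no place for a covariate, and the rule for including age has no criterion, so the choice could be made after the data are seen.

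**Working it through.** **1. Is there a matching step?** Sections 1.2 and 1.3 promise age-matching. Sections 2.0 and 2.3 give a shared 45-65 range, prior-test requirements for controls, and separate recruitment routes. They give no matching ratio, age caliper, age band, or order of enrolment that would let controls be chosen to fit cases.

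**2. Does the analysis supply it?** The t-tests in 2.8 cannot adjust for age. The ANOVA could, but only under the open-ended covariate sentence. The other two covariates in that sentence do not exist for controls, so it does not work as an adjustment plan for the group comparison.

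**3. The plan's own figures (section 2.2).** With n per group = 2(1.96 + 0.84)² × SD² / difference²:
- Strain: 2 × 7.85 × 5.2² / 6.49² = 10.1, so 11, as stated.
- AEMD, SD 7: 2 × 7.85 × 7² / 7.7² = 13.0, so 13; the noncentral t gives 15.
- AEMD, pooled SD √[(9.1² + 4.9²)/2] = 7.31: 14.1, so 15, as stated.

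The sample size is not at issue.

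**4. Illustration of a systematic gap.** Inputs from 2.2: 15 per group, AEMD SD 7.31, strain SD 5.2, differences 7.7 ms and 6.49 points. Assumptions not in the documents: a systematic gap of 3 years, slopes of 0.2-0.6 ms/year (AEMD) and 0.1-0.3 points/year (strain), both acting in the direction that mimics an AF effect.

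Shift = gap × slope. Noncentrality = shift / (SD × √(2/15)). The false-positive rate is the probability that a noncentral t with 28 df falls outside ±2.048.

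| Outcome | Shift | Share of planned difference | Noncentrality | False-positive rate |
|---|---|---|---|---|
| AEMD, low | 3 × 0.2 = 0.6 ms | 8% | 0.6/2.67 = 0.22 | 5.5% |
| AEMD, high | 3 × 0.6 = 1.8 ms | 23% | 1.8/2.67 = 0.67 | 10.0% |
| Strain, low | 3 × 0.1 = 0.3 | 5% | 0.3/1.90 = 0.16 | 5.3% |
| Strain, high | 3 × 0.3 = 0.9 | 14% | 0.9/1.90 = 0.47 | 7.4% |

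**5. Chance gaps.** If both groups are drawn from the same age distribution (assumed uniform over 45-65), age variation is part of the outcome SD and is already in the standard error. Simulating this with 15 per group, total SD 7.31 and slopes of 0.2 and 0.6 ms/year leaves the false-positive rate at 5%, to within about 0.1 point.

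**6. Price of adjusting.** The noncentrality for the age-adjusted group effect is (7.7/SD) / √[(2/15)(1 − r²)(1 + g²/4)] on 27 df. Here r is the within-group age-outcome correlation and g the age gap divided by the age SD (assumed 20/√12 = 5.77). With SD 7:
- The unadjusted t-test has power 0.83.
- Adjusted, with no age gap: 0.83 at r = 0, rising to 0.92 at r = 0.5.
- Adjusted, with a 3-year gap: 0.80 to 0.90 over the same range of r.
- Adjusted, with a 5-year gap: 0.76 to 0.87.

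**The case against.** The documents are silent on how controls are chosen from the list; they do not exclude choosing by age. The shared range is a partial control, telephone screening follows the first contact, and age is the first covariate named. This stands in part. A reader might infer that the groups will not be age-matched, but the documents support only that no described procedure assures it.

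A reader might also infer that the primary analysis is an unadjusted t-test. Section 2.2 names primary outcomes, but 2.8 labels no test as primary. Hypothesis 1 covers rest and exercise, so the repeated-measures ANOVA is a plausible main analysis for strain, and it can carry age. The fair criticism is the lack of a criterion for including age.

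A third tempting reading is that chance alone makes the t-test misleading. With ages uniform over 45-65 and 15 per group, a mean gap above 1.96 × 5.77 × √(2/15) = 4.1 years would arise in 5% of samples. But chance gaps of this kind do not inflate the error rate (step 5 of the working), so they are no evidence of bias.

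Finally, the size of any bias is assumption multiplied by assumption. Patients with AF were older in both planning cohorts in 2.2 (51.78 v 48.97 and 48.3 v 45.2 years, gaps of 2.8 and 3.1). Those were not athlete cohorts, and one AF group had an age SD of 11.1, much wider than a 45-65 range would give. Nothing in the documents gives the ages of the email-list cohort or of the likely AF recruits, or even the direction of a gap. This objection stands as to size. It does not remove the mismatch between the stated property and the described procedures.

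**Conclusion.** The point holds as a gap between what the plan claims and what its procedures assure. It rests on the text alone and needs no assumption about age effects. The consequence for inference is conditional: the comparison is biased only if the groups differ systematically in age and the outcomes depend on age. Under the 3-year gap and the slopes assumed above, the effect is modest, up to 23% of the planned AEMD difference and 14% of the planned strain difference. At the low end it is negligible. It is worth correcting because the correction is cheap and removes a decision that could otherwise follow sight of the data.

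**What to change.** In section 2.8, replace the t-tests for reservoir strain and intra-left AEMD by a linear model (ANCOVA) with group and age as fixed terms. Include age in the repeated-measures ANOVA as well, and take it out of the list of covariates used at discretion.

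In sections 1.2 and 1.3, replace 'age-matched' by 'age-adjusted' or 'of the same age range', unless controls are actually invited by age to mirror the enrolled athletes with AF.

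The cost is one degree of freedom. At 15-17 analysable per group the effect on power is small, and power rises if age explains part of the outcome. It falls below 0.80 only with a large age gap and a weak age-outcome correlation (for example 0.76 at 15 per group with a 5-year gap and r = 0). No change to the planned recruitment of 17 per group is called for on this account.

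Inviting controls by age band is optional. The size of the list is not given, 17 per group over four bands is about four athletes per band, and control recruitment would have to wait on AF recruitment.

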2.4 Methods

General Procedures

All participants will be assessed at the same time of day. Participants will be asked to abstain from exercise on the day before and the day of each study visit.

Visit One: Participant Screening/Consent/ Graded Exercise Testing /

Echocardiography

The first visit will take place at the Heart Health Laboratory. Prior to attending the first visit, participants will have received consent forms and a 2-week Exercise Diary through email. Participants will complete consent form and have the opportunity to ask questions as needed upon their first visit, as well as return the 2-week Exercise Diary. Participants will be then familiarized with the procedures of the study. Participants will undergo basic anthropometric assessment to determine body mass (weight and height) and resting blood pressure. Following this, participants will be fitted with a 12-lead ECG and proceed to complete resting and submaximal exercise echocardiography, performed by a trained sonographer. Emphasis will be on left atrial volume, phasic function and AEMD. Exercise will be on a semi-recumbent cycle ergometer designed for stress echocardiography (Ergoline 1200EL). Imaging will be performed at rest, followed by a two-minute warm up. Participants will then cycle at 100 bpm for 5 minutes and at 130 bpm for 5 minutes; imaging will be initiated 2 minutes into each stage. During a 30-min rest period, participants will complete a Lifetime Physical Activity Questionnaire

Participants will then proceed to have a maximal cardiopulmonary exercise treadmill test with a HR monitor (Polar V800).

Visit Two: Resting Signal Averaged ECG/ Cardiac Magnetic Resonance Imaging/Holter Monitor

The second visit will only be required for athletes with atrial fibrillation (AF-ET), as the healthy endurance athletes will have completed this visit during their participation in a previous REB-approved study. Visit 2 will be completed at St. Michael's Hospital. Prior to attending this visit, participants will undergo venipuncture by trained phlebotomist for assessment of serum creatinine and calculation of GFR to confirm normal kidney function, required for LGE administration (see below). On the day of, participants will first have a standard signal averaged ECG performed. Following this, subjects will undergo resting cardiac imaging using (cMRI) (Siemens MAGNETOM Skyra 3.0T with TIM and DOT technology) by a trained technician. Proceeding cMRI, participants will be fitted for a 48 hour Holter monitor that will assess cardiac rhythm over 2 days (at home), in which participants will refrain from exercise for the first day, and will complete a typical bout of exercise on the second day.

2.7 Detailed Procedures

2.7.1 Graded Exercise Testing

A graded exercise test will be completed at the Heart Health Laboratory. Maximal oxygen consumption (VO₂MAX) will be determined by indirect calorimetry obtained during graded exercise testing on a motorized treadmill (Full Vision TMX4125) using a calibrated metabolic cart (VMax Encore, CareFusion). Expired gases will be collected and averaged over 10 second intervals. Maximal effort will be confirmed by a plateau of

oxygen uptake despite increasing workrates and secondary criteria will include achievement of age- predicted maximum heart rate $(208 - (0.7 \times \text{AGE})) \times [60]$ and a respiratory exchange ratio > 1.15 . Standard measures of expired gases will be performed. Continuous measures of HR during exercise using a electronic heart rate monitor (Polar Inc.) will be integrated to data recording of the metabolic cart. A 3-lead ECG will be established and recorded every minute. A physician will be on site during exercise testing with an AED located within 5 meters.

2.7.2 Resting and Submaximal Echocardiography

Participants will undergo transthoracic echocardiography (GE E9 Imaging System) at the Heart Health Laboratory, provided the individual is in sinus rhythm. Imaging will be performed by a trained sonographer, and images will be obtained according to the criteria of the American society of echocardiography guidelines. Subjects will be initially placed in a supine position on a purpose-built imaging/cycle ergometer (Ergoline 1200E), for assessment of resting cardiac structure and function. During exercise, subjects will be repositioned to a 45 degree semi-upright position with minor left caudal tilt to optimize imaging. Cycle ergometry will be performed concurrent with echocardiography.

For all acquisitions, two-dimensional apical (two and four chamber view) and parasternal (long and short axis) imaging will be performed for dimensional and functional parameters of the atria and of the ventricles at a frame rate of 60-80 (fps). Volume and size measurements will be normalized to body surface area. Echocardiograph imaging will primarily be used for functional measures at rest and exercise; structural assessment of chambers will be determined using cMRI. Emphasis

will be on left atrial reservoir function, as this parameter has provided robust insight into AF-associated impairment even in the presence of normal LA size. Left atrial volumes will be measured at different time points of the cardiac cycle. Atrial maximal volume (LA max) will be measured at the end of ventricular systole, prior to the opening of the mitral valve; atrial pre-A volume (LA PRE-A) will be measured prior to onset of atrial contraction (beginning of P wave); atrial minimal volume (LA min) will be measured at the closure of the mitral valve. Accordingly, LA phasic volumes and emptying fractions will be calculated. Left and right ventricular volumes and ejection fraction will be calculated by the modified bi-plane Simpson's method. Images for LA strain will be obtained using Speckle Tracking echo. Strain measures will include global longitudinal strain, peak atrial longitudinal strain, and atrial phasic strain (reservoir: during ventricular systole, conduit: during early ventricular diastole and booster: during late ventricular diastole). Left ventricular strain during ventricular systole, early diastole and late diastole will also be measured. Pulsed-wave Doppler interrogation of transmitral flow will be obtained at the septal and lateral mitral annulus to determine flow velocities during early (E) and late (A) diastole, as well as the E/A ratio. Tissue Doppler imaging will also be performed at the septal and lateral mitral annulus to determine myocardial systolic (Sm), early diastolic (Em) and late diastolic (Am) velocities. Care will be taken to minimize gain and all analyses of DTI and Doppler flow patterns will be conducted according to current ASE guidelines⁸⁴⁻⁸⁶. The collection of these images will allow us to calculate intracardiac volumes and indices of diastolic and systolic function.

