2.7.3 Atrial Electromechanical Delay

Tissue Doppler Echocardiography will be performed by transducer frequencies of 3-4MHz, adjusting the spectral pulsed Doppler signal filters until a Nyquist limit of 15-20cm/s and using the minimal optimal gain. The monitor sweep speed will be set to 50-100mm/s to optimize the spectral delay of myocardial velocities. In apical 4-chamber view, the pulsed Doppler sample volume will be placed at the lateral and septal sides of the mitral annulus and the right-ventricular (RV) tricuspid annulus to obtain tissue Doppler velocities. The time intervals from the onset of the P wave (ECG) to the beginning of the Am wave (on echo) will be measured from the lateral mitral annulus (lateral PA), septal mitral annulus (septal PA), and RV tricuspid annulus (tricuspid PA). The timing of mechanical activation of each sample point is dependent on the distances of each point to the sinoatrial node (SA). Accordingly, the RV tricuspid annulus is the earliest (closest) and the lateral mitral annulus is the latest (farthest) point to be activated by impulses from the SA node. The difference between any two reference points reflects the mechanical delay between these two points Inter-AEMD will be defined as the difference between the lateral PA and tricuspid PA, intra-right AEMD will be defined as the difference between the septal PA and tricuspid PA, and intra-left AEMD will be defined as the difference between the lateral PA and septal PA.

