2.7.4 Cardiac Magnetic Resonance Imaging

All athletes with AF will undergo resting cardiac magnetic resonance imaging (cMRI) at St. Michael's hospital, following methods used for previous REB-approved study). MRI will be performed supine in a 3.0T scanner (Siemens MAGNETOM Skyra 3.0T with TIM and DOT technology); images will be obtained on end-expiration breath holds. Vertical long-axis cine images will be prescribed from axial scout images by aligning the left ventricular (LV) apex with the center of the mitral valve. From these LV long-axis images, the horizontal long-axis plane will be obtained by aligning the midpoint of the left ventricular apex and mitral valve. These pilot 4-chamber and 2-chamber views provide the reference images on which a stack of contiguous short-axis slices will be prescribed, covering the left atrium and left ventricle. Depending on the LV long-axis length, 8-12 contiguous slices will cover the entire left ventricle. Providing normal creatine levels are verified (see above), delayed enhancement MRI will be acquired 10 minutes after contrast agent injection of gadolinium (0.1 mmol/kg body weight, Multihance, Bracco Diagnostic Inc, Princeton, NJ) (MRI contrast agent does not contain iodine and does not damage the kidneys. Subjects refusing gadolinium will still be studied. Imaging will be used for cardiac structure and volumetric assessments of the

atria and ventricles (max and min volume, EDV and ESV). All data analysis will be performed using CMR42 (Circle Imaging, Calgary, Canada). End-diastolic frames are defined as the image with the largest ventricular volume in each series, and end-systolic as the image with the smallest volume. Endocardial and epicardial borders on these frames will be manually traced. From this data, LV and RV ejection fraction, end diastolic/end systolic and stroke volume indices will be calculated. Manual tracing of endocardial borders of short-axis images at atrial end-diastole and atrial end-systole will allow for calculation of LA end-diastolic volume and end-systolic volume.

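### No masking to group is stated for reading LA reservoir strain or AEMD; separately, the controls' cMRI and signal-averaged ECG come from an earlier study and no joint re-read is planned

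*Combined protocol and SAP*

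**What the plan says.** **Primary outcomes.** Section 2.2 names LA reservoir strain and AEMD as the primary outcomes of the two hypotheses. Both come from the Visit One echocardiogram (2.4), which both groups undergo in this study. Section 2.7.2 states "Imaging will be performed by a trained sonographer", refers to echocardiography society guidelines, and obtains LA strain by speckle tracking. For AEMD, section 2.7.3 states "The time intervals from the onset of the P wave (ECG) to the beginning of the Am wave (on echo) will be measured" at three annular sites. It defines intra-left AEMD as lateral PA minus septal PA.

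**Visit Two measures.** Only the AF group attends Visit Two, because "the healthy endurance athletes will have completed this visit during their participation in a previous REB-approved study" (2.4). The H-ET cMRI, SAECG and Holter data are therefore earlier data. For cMRI, section 2.7.4 states "Endocardial and epicardial borders on these frames will be manually traced". Section 2.7.4 follows the earlier study's methods, and section 2.6.3 says SAECG acquisition and analysis will match what the controls received.

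**Not stated anywhere.** The document does not mention masking of any reader, coded files, a reading order, a joint reading of both groups' recordings, or a check of observer agreement. Section 2.2 expects that "poor imaging quality lead to unanalyzable data may occur in 10-15% of the sample" but does not say who decides this, or whether that person knows the group.

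**The concern.** The groups are recruited by different routes (2.0, 2.3), so study staff know who has AF. Section 1.3 predicts the direction of each result: lower reservoir function and longer AEMD in the AF group. A reader who knows the group therefore also knows which way each measurement is expected to move. A systematic shift in reading between groups would be added to the estimated difference. The t-tests and repeated-measures ANOVA in section 2.8 cannot separate it from a true effect.

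For cMRI and SAECG there is a second problem. All control data come from the earlier study and all AF data from this one, so a term for period would be collinear with group. This matters because cMRI is the designated structural assessment (2.7.2) and so bears on the premise of similar atrial size in hypothesis 2. SAECG is the only described source of a P-wave duration measurement, which the exploratory correlation with AEMD needs (1.2).

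**Working it through.** **1. Planned effects (2.2).** AEMD: "21.8 ± 9.1 ms in AF patients and 14.1 ± 4.9 ms in controls (difference of 7.7 ± 7 ms". Strain: "the mean difference between groups was 6.49 ± 5.2". Alpha is 0.05 and power 0.80; two-sided testing is assumed because it fits the stated sizes.

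**2. Reproducing the plan's sample sizes.** Normal approximation: n per group = 2(1.960 + 0.842)² SD² / difference².
- Strain: 2 × 7.849 × 5.2² / 6.49² = 10.1, so 11. The t-based figure is 11.12. The plan says 11.
- AEMD, SD 7: 2 × 7.849 × 7² / 7.7² = 12.97, so 13. The t-based figure is 14.002, so 15 when rounded up. The plan says 15.
- AEMD, SD pooled from the group values: √[(9.1² + 4.9²)/2] = 7.31. The normal approximation gives 14.1, so 15.

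The stated sizes reproduce, and masked reading does not change them.

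**3. What kind of reading shift reaches intra-left AEMD.** It equals (lateral Am onset − P onset) − (septal Am onset − P onset). A systematic shift in marking P onset, or a shift in marking Am onset that is the same at both sites, cancels even if it differs between groups. Only a net shift in the lateral-minus-septal difference that also differs by group survives. At the sweep speed of 50–100 mm/s in section 2.7.3, the whole planned 7.7 ms is 0.39–0.77 mm on the trace, and 2 ms is 0.1–0.2 mm.

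**4. False-positive rate under an assumed net shift b with no true difference.** Two-sided t-test, 15 per group, 28 degrees of freedom, critical value 2.048, noncentrality b / (SD × √(2/15)).

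| Outcome | SD | Net shift b | Share of planned effect | Noncentrality | False-positive rate |
|---|---|---|---|---|---|
| AEMD | 7.31 ms | 1 ms | 13% | 0.37 | 6.5% |
| AEMD | 7.31 ms | 2 ms | 26% | 0.75 | 11.2% |
| AEMD | 7.31 ms | 3 ms | 39% | 1.12 | 19.2% |
| Strain | 5.2 points | 1 point | 15% | 0.53 | 8.0% |
| Strain | 5.2 points | 2 points | 31% | 1.05 | 17.4% |

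With the plan's rounded AEMD SD of 7 ms, the three AEMD rates are 6.7%, 11.8% and 20.5%.

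**5. cMRI and SAECG.** The plan gives no SDs for these, so the shift is expressed in SD units. A period shift of 0.2, 0.3 or 0.5 SD, with 15 per group, gives about 8%, 12% or 26%.

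Every shift in steps 4 and 5 is an assumption. The documents give no figure for reader error or drift.

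**The case against.** Several points on the other side stand.

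- **Manual reading.** A reader might infer that strain, AEMD and cMRI are all measured by hand. The documents show this only for cMRI borders. Strain uses speckle tracking, and the way AEMD intervals are marked is not described. Reader judgement is likely in both, but that is inference.
- **Historical controls.** A reader might also infer that the earlier-study controls threaten the primary contrasts. They do not: strain and AEMD are acquired in both groups in this study, so between-study drift cannot reach them.
- **AEMD arithmetic.** Not every cursor shift enters the contrast. The subtraction in step 3 removes the common part, so the tabulated net shifts are harder to reach than equal shifts in a single interval.
- **Matched methods.** Sections 2.6.3 and 2.7.4 commit to the earlier methods, and section 2.7.4 names one cMRI analysis package. This reduces drift. It does not put old and new recordings before the same reader together, and it does not conceal group.
- **Size.** The bias is hypothetical, and a 1 ms net shift barely moves the error rate.

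None of this supplies masking. Training and guidelines standardise technique but do not hide which group a recording belongs to.

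**Conclusion.** The point holds in two separate parts. First, the plan states no masking for reading the two primary outcomes, while group is known and the hypotheses are directional, so reader expectation can bias those contrasts. Second, for cMRI and SAECG only, period coincides with group and no joint re-read is planned; matched methods lessen this without removing it.

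The size of any bias cannot be estimated from the documents. Under the assumed net shifts, the false-positive rate is about 6.5% to 19% for AEMD (1 to 3 ms) and 8% to 17% for strain (1 to 2 points), against a nominal 5%. The documents do not show that bias is present or that any group difference would be an artefact. They show that the plan as written could not tell the two apart. The change should be made before reading begins, because a shift already built into unmasked readings cannot be removed by analysis.

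**What to change.** In sections 2.7.2 to 2.7.4 and the SAECG section (2.6.3), add the following:

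- Store all echo, tissue Doppler, cMRI and SAECG files under a study code, with group, identity and acquisition date removed. Dates matter because the H-ET cMRI and SAECG come from the earlier study, so a date could reveal group.
- After the last participant, shuffle AF-ET and H-ET files. One existing reader per modality measures them offline in one batch, unaware of group. Preferably this is not the person who screened or scanned the participants.
- Make the decision that an image is unanalyzable within the same masked read.
- Re-trace the stored H-ET cMRI and re-analyse the stored H-ET SAECG in that batch if the raw files are retained. The documents do not say whether they are. If they are not, report the cMRI and SAECG group comparisons with that limitation.
- State that masked reading cannot remove differences arising at acquisition, such as sonographer settings or the earlier scan period.

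The cost is the coding work, re-reading up to 17 stored H-ET data sets, and a later readout. No participants, visits, procedures or additional readers are needed, provided each modality has an existing reader who can be kept unaware of group.
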